Integrated Alcohol Disorder and PTSD Treatment

NCT01601067

04/14/2016

Objectives

The primary aim will be to evaluate the effects on alcohol use and PTSD symptoms of an exposure-based integrated AD and PTSD intervention (i.e., COPE) when compared to a present-focused coping skills intervention (i.e., Seeking Safety [SS]) in male and female Veterans with comorbid AD and PTSD. Hypotheses for the primary aim are:

1. At post-treatment, both groups will show reductions in alcohol use, but COPE will demonstrate greater reduction in PTSD symptoms than SS.
2. At the 2nd and 3rd post treatment follow up assessment ,COPE will have significantly fewer percent drinking days than SS.
3. At the 2nd and 3rd post treatment follow up assessment ,COPE will continue to have lower PTSD symptom scores.

Design.

The proposed study will be a randomized controlled trial comparing Concurrent Treatment of PTSD and Substance Use Disorders using PTSD (COPE) to Seeking Safety (SS) for the treatment of male and female Veterans with AD/PTSD. 178 participants will be enrolled through the San Diego VA and randomized at the individual level. Measures will occur at baseline, post-treatment, and two post treatment follow up assessments. Participants will complete the 2nd post treatment assessment interview and set of questionnaires 3 months after the 1st post treatment appointment. Participants will be scheduled for their 3rd and last post treatment interview 3 months after completing their 2nd post treatment assessment. All procedures will be done for research purposes.

Methods

All work will be carried out at the SAMI outpatient program and PTSD clinics of the Veteran Affairs San Diego Healthcare Systems (VASDHS). Random permuted blocks will be used which ensure exactly equal treatment numbers at certain equally spaced points in the sequence of patient assignment. Randomization will be stratified by gender to ensure a balanced number of males and females are in each treatment group.

The Timeline Follow-back Procedure (TLFB50) will be employed at baseline, post-treatment, 5-month, and 8-month follow up to evaluate drinking and all drug use during the 30 days preceding each interview.

The Clinician-Administered PTSD Scale for DSM-V(CAPS54,55) is a standard semi-structured interview used to assess PTSD diagnosis and severity. As part of the CAPS, a list of potentially traumatic events is given to respondents.

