Integrated Alcohol Disorder and PTSD Treatment

NCT01601067

09/03/2011

Primary Outcome Analyses.

6.H.3. Primary Outcome Analyses. The first primary aim is to evaluate if I-PE will demonstrate greater reduction in PTSD symptoms than SS at post treatment. The statistical model will be a random intercept regression model with treatment condition (I-PE, SS) and a linear term for time (0, 2 months). The primary test of the treatment conditions will be treatment x time interaction effect. We will also test the extent to which gender moderates treatment effect. The model can be expanded to determine an adjusted intervention effect by including additional covariates(e.g., age, ethnicity). This model provides maximum likelihood (ML) parameter estimates; allowing modeling of the covariance error structure data across assessment points.⁹¹

The second primary aim is to evaluate if I-PE will result in greater percent days abstinent (PDA) from substance use at 5 and 8-month follow-up. The statistical model will be a random intercept regression model with treatment condition (I-PE, SS) and a linear term for time (0, 2, 5, 8 months). The primary test of the treatment conditions will be the treatment x time interaction effect. A quadratic effect of time will also be tested to model potential decaying treatment effects. We will test the moderating effect of gender on the treatment effect by testing a treatment x time x gender interaction term in the model. Additional covariates can also be added to the model to determine an adjusted intervention effect.

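### The second primary aim is about months 5 and 8, but the primary test is a single linear treatment-by-time slope over months 0 to 8, and no month-5 or month-8 comparison is prespecified

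*SAP*

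**What the plan says.** In SAP section 6.H.3 the second primary aim is "greater percent days abstinent (PDA) from substance use at 5 and 8-month follow-up". Hypothesis 2 under Objectives in the protocol points to the same two visits: "At the 2nd and 3rd post treatment follow up assessment ,COPE will have significantly fewer percent drinking days than SS". For alcohol, hypothesis 1 predicts only that both arms improve by the end of treatment: "At post-treatment, both groups will show reductions in alcohol use, but COPE will demonstrate greater reduction in PTSD symptoms than SS". Under Methods, the timeline follow-back "will be employed at baseline, post-treatment, 5-month, and 8-month follow up", so a separate 30-day drinking measure exists at each target month.

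The analysis in 6.H.3 is a "random intercept regression model with treatment condition (I-PE, SS) and a linear term for time (0, 2, 5, 8 months"). It continues: "The primary test of the treatment conditions will be the treatment x time interaction effect". The next sentence adds: "A quadratic effect of time will also be tested to model potential decaying treatment effects". The supplied text gives no treatment contrast at month 5, at month 8 or averaged over both, and no rule for turning two months into one claim.

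**The concern.** The aim asks whether the arms differ at two named visits. The test asks whether the arm difference changes along a straight line from baseline to month 8. The two agree only if the difference starts at zero and grows linearly. If the benefit is already present at the end of treatment, the line absorbs part of it into the fitted baseline difference and the slope shrinks. If the benefit then fades, as the SAP itself contemplates, the slope shrinks further. A significant slope would therefore not establish a difference at month 5 or month 8, and a null slope would not rule one out. Month contrasts chosen after the data are seen would leave the primary claim unprotected.

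**Working it through.** **Inputs from the documents.** Visits at 0, 2, 5 and 8 months and the linear model (SAP 6.H.3); 178 participants in equal arms (protocol, Design and Methods), hence 89 per arm. I take I-PE in the SAP to be COPE in the protocol. The documents give no power calculation to reproduce.

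**Assumed, not in the documents.** Two-sided 0.05, complete data, normal approximation, equal correlation r = 0.5 between visits, and an effect d of 0.5 SD (0.3 SD as a check).

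**What the slope estimates.** The mean visit time is 15/4 = 3.75. The centred times are −3.75, −1.75, 1.25 and 4.25, with sum of squares 36.75. With complete data in a random-intercept model:

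slope = (−3.75·d0 − 1.75·d2 + 1.25·d5 + 4.25·d8) / 36.75,

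where d0 to d8 are the arm differences, positive when they favour I-PE. Month 8 has 4.25/1.25 = 3.4 times the weight of month 5, and month 2 counts against treatment. A difference at month 2 alone gives a slope of −1.75d/36.75 = −0.048d per month, although nothing differs at either target month.

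**Fitted arm differences.** Fitted value at t = mean of the four differences + slope × (t − 3.75). No n, SD or correlation is needed.

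| True pattern (months 0, 2, 5, 8) | Mean | Slope | Fitted at 0, 2, 5, 8 |
|---|---|---|---|
| Protocol-implied: 0, 0, d, d | 0.5d | 5.5d/36.75 = 0.150d | −0.06d, 0.24d, 0.69d, 1.14d |
| Sustained: 0, d, d, d | 0.75d | 3.75d/36.75 = 0.102d | 0.37d, 0.57d, 0.88d, 1.18d |
| Halved: 0, d, 0.75d, 0.5d | 0.5625d | 1.3125d/36.75 = 0.036d | 0.43d, 0.50d, 0.61d, 0.71d |

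In the halved pattern the fitted difference rises after month 2 while the true one falls.

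**Power.** z = effect/SE, with both tails counted. In SD units at n = 89 and r = 0.5:
- Slope: variance (2/n)(1 − r)/36.75, SE 0.0175.
- Average month-5/8 change, weights (−1, 0, ½, ½): variance (2/n)·1.5(1 − r), SE 0.130.
- Slope with common baseline: weights (−3, −1, 2, 5)/48, SE 0.0153. Month 2 is still negative.
- Average with common baseline: weights (−½, 0, ½, ½), variance (2/n)·0.5, SE 0.106.

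For example, in the halved pattern at d = 0.5 the unconstrained slope is 0.0357 × 0.5 = 0.0179, so z = 1.02. The change contrast is 0.625 × 0.5 = 0.3125, so z = 2.41.

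| Pattern | d | Slope vs average, no constraint | Slope vs average, common baseline on both |
|---|---|---|---|
| Protocol-implied | 0.5 | 99 vs 97% | 99.7 vs 99.7% |
| Sustained | 0.5 | 83 vs 97% | 98 vs 99.7% |
| Halved | 0.5 | 17.5 vs 67% | 53 vs 84% |
| Linear growth to d at month 8 | 0.5 | 95 vs 88% | 98 vs 97% |
| Protocol-implied | 0.3 | 73 vs 64% | 82 vs 81% |
| Sustained | 0.3 | 42 vs 64% | 69 vs 81% |
| Halved | 0.3 | 9 vs 30% | 23 vs 42% |
| Linear growth to d at month 8 | 0.3 | 57 vs 47% | 69 vs 63% |

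A simulation of 20,000 trials per case at d = 0.5 agreed to within about one percentage point.

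**Sensitivity, halved pattern, d = 0.5.** As r goes from 0.3 to 0.7, the slope goes from 14 to 26% and the average from 53 to 87% without a constraint. With a common baseline the slope goes from 64 to 51% and the average from 80 to 93%. With 62 per arm (about 30% loss) and r = 0.5, the figures are 14 vs 52% and 40 vs 69%.

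**Combining the months** (common baseline). Under the protocol-implied pattern the average has 99.7% power at d = 0.5 and 81% at d = 0.3. Requiring both months, each at 0.05, has 94% and about 45%. If an effect of 0.5 SD exists at only one of the two months, the average is still significant 65% of the time.

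**The case against.** The strongest reply is the quadratic sentence. A decaying treatment effect can only be modelled through a treatment-by-time-squared term, so the SAP arguably plans one. Under the same assumptions, without a baseline constraint, that interaction test would have about 80% power in the halved pattern. The fitted curve would be 0.12d, 0.72d, 0.97d and 0.43d, so it would turn down by month 8. The worst figures above therefore describe the primary test alone, not everything the SAP might run. But the SAP names no such interaction, does not make it primary and gives it no decision rule. A significant curvature term is also not a comparison at month 5 or month 8.

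Second, under the course the protocol implies, the slope is at least as powerful as the contrast. That is true. The power losses need a difference already present at month 2, which hypothesis 1 does not predict for alcohol. Even the absence of a month-2 difference is an inference from its wording.

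Third, part of the gain from the recommended model comes from the common baseline alone: it moves the slope from 83 to 98% (sustained) and from 17.5 to 53% (halved). The like-for-like comparison is the right-hand column of the power table.

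Fourth, percent days is a bounded outcome and every power input is assumed. That limits the percentages, not the slope weights. Finally, the SAP supplied is an excerpt. Month differences could be read off the fitted line, but the text does not say so, and they would depend on linearity.

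**Conclusion.** The concern holds for the supplied text and should be fixed. It is first a mismatch between the stated question and the primary test. That part rests on the wording and on slope weights that need only complete data. The loss of power is conditional: none under the protocol-implied pattern or linear growth, little to moderate if the benefit is present at month 2 and sustained, and large if it then decays. On equal terms with a common baseline at d = 0.5, the decay gap is 53% against 84%. Those percentages depend on the assumed effect size, correlation, complete data and normality. The misfit at the target months does not: 0.69d and 1.14d where the truth is d at both, and a rising fit where the truth falls.

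**What to change.** Make the treatment difference at months 5 and 8 the primary test of the second aim, for example as their average, and report each month with its 95% CI. State whether the claim rests on the average or requires both months, since the average can be significant with an effect at only one.

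Estimate it from a model with categorical time, treatment-by-visit terms and a common baseline mean. The first-aim paragraph of 6.H.3 already describes the likelihood approach as "allowing modeling of the covariance error structure data across assessment points", so modelling the covariance is within the plan's scope. A model with treatment-by-time and treatment-by-time-squared terms and a common baseline also serves for the average: 99.6, 99.8, 85 and 97% power for the four patterns in table order at d = 0.5 and r = 0.5. Its single-month estimates are less exact. In the halved pattern it fits 0.92d and 0.36d where the truth is 0.75d and 0.50d. Keep the linear slope and the treatment-by-quadratic trend as secondary.

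The cost is SAP wording and three more fixed effects: four visit means plus three treatment differences make seven, against four in the linear model, with 178 participants. If the effect truly grows linearly, power falls from 98 to 97% at d = 0.5 and from 69 to 63% at d = 0.3 with a common baseline on both. Without that constraint the falls are 95 to 88% and 57 to 47%, and the plain change contrast also gives up power under the protocol-implied pattern (99 to 97%; 73 to 64%). No new data are needed.

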The primary outcomes will be tested using an intent-to-treat framework. If the extent of missing data is small and the data appear to be consistent with a missing-at-random model (MAR), then the maximum-likelihood analysis using all randomized cases and the observed data is an appropriate method for handling the missing data. In the MAR model the missingness can be a function of the observed covariates and observed outcomes. The MAR assumption is plausible in treatment situations, even in studies such as substance abuse in adolescents.⁹² The critical element when conducting MAR-based analyses is to include variables related to the missingness in the statistical model.⁹² Potential variables we will measure that may be related to study drop out are group assignment, social and familial support, employment status, and income. As a check on the sensitivity of our conclusions to the assumption that the missing data are MAR we will conduct pattern-mixture modeling, which is appropriate with data that is likely MAR.⁹³ The distinction between ignorable (MAR) and non-ignorable missingness (missing not at random; MNAR) is generally not empirically testable and we acknowledge the possibility that data may be missing not at random. Therefore, we propose to perform MNAR sensitivity analyses using pattern mixture models. With 3 follow-up assessment points there are 9 potential missing data patterns that can emerge. Some patterns will likely have small numbers of cases precluding parameter estimation for these patterns separately. In this case we will apply the Hedeker and Gibbons (1997) approach that combines missing data patterns to estimates model parameters that are conditional on the missingness using a binary variable in the model to denote missing data at one or more time points.

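### The four-visit drinking model names only a random intercept; a covariance structure should be pre-specified, because the treatment x time test can be too liberal if that model is fitted as named

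*SAP*

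**What the plan says.** SAP 6.H.3 treats the two primary aims in consecutive paragraphs.

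- **First aim (PTSD symptoms, two visits).** A random intercept model at 0 and 2 months. The paragraph closes by saying that maximum likelihood is used, "allowing modeling of the covariance error structure data across assessment points". No structure is named.
- **Second aim (percent days abstinent, four visits).** The model is specified afresh as a "random intercept regression model with treatment condition (I-PE, SS) and a linear term for time (0, 2, 5, 8 months"). On which coefficient decides the aim, the SAP is explicit: "The primary test of the treatment conditions will be the treatment x time interaction effect". It then adds a curvature term: "A quadratic effect of time will also be tested to model potential decaying treatment effects". Gender moderation is tested by a three-way interaction in the same model.

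The posted text names no random slope, residual correlation structure or robust standard error for the second aim. It also does not say that the random intercept is the only covariance term.

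**The concern.** A random intercept with independent residuals implies that every pair of visits is equally correlated and that everyone in an arm shares one rate of change. Over eight months of drinking data either implication may fail. Some participants improve while others relapse, and visits two or three months apart may agree more closely than visits eight months apart. The primary test compares slopes, and its standard error relies directly on this assumption. If the assumption fails, the interval for the second primary outcome is too narrow and a true null is rejected too often.

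The quadratic term does not help, because it alters the mean and not the covariance. Treating time as categorical would not help for the same reason. The first aim is not exposed in this way: with two visits and complete data there is only one within-person contrast, and the model estimates its variance directly.

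**Working it through.** **Inputs from the documents.** Visits at 0, 2, 5 and 8 months, and the treatment by time test (SAP 6.H.3). Sample size: "178 participants will be enrolled through the San Diego VA and randomized at the individual level" (Protocol, Design). Allocation: "Random permuted blocks will be used which ensure exactly equal treatment numbers" (Protocol, Methods), taken as 178/2 = 89 per arm. Missing data: "maximum-likelihood analysis using all randomized cases and the observed data is an appropriate method" when loss is small and consistent with MAR (SAP, missing-data paragraph).

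**Assumed, because not stated.** Two-sided 5% level, complete data, and every variance and correlation. The plan has no figure of its own to reproduce here.

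**Formulas.** Mean time is 15/4 = 3.75. The deviations d are -3.75, -1.75, 1.25 and 4.25, so S = 14.0625 + 3.0625 + 1.5625 + 18.0625 = 36.75. With complete data the interaction estimate is the difference in mean per-person least-squares slopes. For true covariance V:

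- true slope variance per person = d'Vd / S²
- variance the model reports = s² / S, where s² = [tr(V) - 1'V1/4] / 3 + L, and L is lack of fit of the linear mean
- variance ratio R = (d'Vd / S) / s²
- actual size = 2[1 - Φ(1.96/√R)]

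The number per arm cancels from R, so a larger trial would not cure the problem.

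**Compound symmetry.** Numerator and s² both equal the residual variance σ². R = 1 and size is 5.0%.

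**Random slope with variance τ².** R = (σ² + τ²S) / (σ² + τ²S/3). Set baseline variance to 1 with σ² = 0.5, and let the slope contribute 25% of baseline variance at month 8. Then τ² = 0.25/64 = 0.0039 and τ²S = 0.1436, so R = 0.6436/0.5479 = 1.175, √R = 1.084 and size is 7.1%. Equivalently, if p is the between-person share of slope variance, R = 1/(1 - 2p/3); p = 0.5 gives R = 1.5 and 11.0%.

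**Serial correlation 0.9 per month.** d'Vd/S = 0.674 and s² = 0.363, so R = 1.86 and size is 15.0%. Adding a constant person effect leaves R unchanged, because it cancels from both parts.

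**Early drop of 1 SD, then flat, linear time only.** The sum of squares left over is 0.75 - 3.75²/36.75 = 0.367, so L = 0.367/3 = 0.122. Under compound symmetry R = 0.5/0.622 = 0.803 and size is 2.9%. With a 3-month serial correlation of 0.5, R = 0.992/(0.608 + 0.122) = 1.358 and size is 9.3%.

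| Assumed truth | Linear mean | 1 SD drop, then flat |
|---|---|---|
| Compound symmetry | 5.0% | 2.9% |
| Slope variance at month 8 = 5% / 10% / 25% of baseline variance | 5.4% / 5.9% / 7.1% | 4.5% (25% case) |
| Same, 50% / 100% | 8.8% / 11.6% | not in closed form |
| Slope share p = 0.2 / 0.3 / 0.5 / 0.6 | 6.8% / 8.0% / 11.0% / 12.9% | not computed |
| Baseline correlation 0.3, follow-ups 0.6 | 6.7% | 4.3% |
| Serial, 3-month correlation 0.3 / 0.5 / 0.7 / 0.9 | 9.9% / 12.5% / 14.7% / 16.7% | 9.3% (0.5), 9.7% (0.7) |
| Serial, 0.8 / 0.9 / 0.95 per month | 12.6% / 15.0% / 16.3% | not computed |

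A 1.5 SD drop brings the 0.5 serial case down to 6.4% and compound symmetry to 1.5%.

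**Check by simulation.** The random-intercept model was fitted by maximum likelihood, 89 per arm, 4,000 runs. Size was 5.4% under compound symmetry, 12.3% and 15.3% for serial correlation 0.5 and 0.7, and 6.8% and 9.3% for the 25% and 50% slope cases. Losing 12% at each visit changed little (11.9% for serial 0.5).

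**Check of the remedy.** Over 20,000 runs with a linear mean, under compound symmetry, serial 0.5 and 0.7, and the 50% slope case, generalised least squares with an unstructured covariance gave 5.0% to 5.6%. A t-test on per-person slopes gave 4.6% to 5.1%.

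**The case against.** A reader might infer that the SAP permits a random intercept and nothing more, and that the primary test therefore rejects a true null well above 5%. The documents support neither step.

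First, the covariance remark can be read as describing the model class, which the second aim shares. With two visits a random intercept already supplies the single within-person correlation, so the remark has most of its content where there are more visits. The posted SAP text also starts at 6.H.3. This stands as far as it goes: other covariance terms are not ruled out. But the remark says what maximum likelihood makes possible, not what will be fitted. On this reading the choice stays open for a primary analysis, which is itself worth closing.

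Second, every figure above 5% rests on assumed components. The serial cases contain no independent visit noise. Mixing such noise with a stable person effect and decaying correlation (baseline correlations about 0.5 to 0.6 at 2 months, 0.3 to 0.5 at 8 months) gave 7.2% to 8.8%. The larger slope shares are also strong assumptions. With σ² = 0.5 and uncorrelated intercepts and slopes, p = 0.6 means slopes add 1.5 x (64/36.75) x 0.5 = 1.31 times the baseline variance by month 8.

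Third, the Protocol's first hypothesis expects both arms to reduce drinking by the end of treatment. An early drop fitted as a straight line enlarges the residual and can bring size to 5% or below. This stands too, but the protection comes from a second misspecification. It shrinks as the mean is modelled better, and it does not remove the inflation under strong serial correlation.

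**Conclusion.** The plan leaves the within-person covariance of a four-visit primary slope test at a random intercept, with no other structure committed to. Fitted that way with independent residuals, the standard error is valid under equal correlation and a linear mean. It is too small if slopes vary or correlation decays, unless poor fit of the linear mean compensates. Across the scenarios tried, size runs from about 1.5% to 17% at an assumed two-sided 5% level. Small to moderate slope variance costs little; large slope variance or strong serial correlation can double or triple the error rate.

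Which case applies cannot be told from the documents. This is therefore an inexpensive improvement that should be made, not an error in the plan as written.

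**What to change.** In SAP 6.H.3, second primary aim, pre-specify an unstructured covariance over the four visits, fitted by REML with Kenward-Roger or Satterthwaite degrees of freedom. Name the fallback if it does not converge: random intercept plus random slope, with participant-clustered standard errors. Use the same covariance for the treatment by time by gender model. State the significance level and sidedness at the same point.

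The cost is a sentence or two of SAP text and a few lines of code, with no new data. Four visits need 4 x 5/2 = 10 covariance parameters, which 178 participants should support. Confidence intervals will be slightly wider in the milder cases. They will be more clearly wider where the random-intercept interval would have been too narrow: by up to about 8% in the 25% slope case (√R = 1.08) and 28% in the 0.5 serial case (√R = 1.28), both with a linear mean.

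### The primary drinking test is built on one linear time term, and the SAP leaves the role of the quadratic open; if both arms improve early and then level off, this costs some power and, with unequal dropout, adds a small bias

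*SAP*

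**What the plan says.** SAP section 6.H.3 (second primary aim) analyses percent days abstinent (PDA) with a random-intercept model that contains the treatment arm and "a linear term for time (0, 2, 5, 8 months"). It then states: "The primary test of the treatment conditions will be the treatment x time interaction effect". The next sentence reads: "A quadratic effect of time will also be tested to model potential decaying treatment effects". Nothing says whether the quadratic stays in the model behind the primary test, what result would bring it in, or whether it is one term shared by both arms or a separate term for each.

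The protocol's Objectives (hypothesis 1) say: "At post-treatment, both groups will show reductions in alcohol use". Post-treatment is the month-2 visit, since the assessments three and six months after it are the 5- and 8-month follow-ups.

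The SAP's missing-data paragraph relies on maximum likelihood under missing at random and lists treatment group among the possible correlates of dropout. It gives no dropout rate.

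**The concern.** A change that has largely happened by month 2 and then levels off is not a straight line over 0-8 months. If the shared time course is modelled as straight, two things follow.

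- **Standard error.** The common misfit goes into the residual. With complete data the treatment x time estimate is unaffected, but its standard error is too large and the test is conservative.
- **Bias.** If the arms lose different numbers of participants, each arm's best straight line rests on a different mix of visits. The arm with more loss leans more on the steep 0-2 month stretch and looks better, even with identical true means at every visit and dropout that depends on arm alone. Likelihood under missing at random does not protect against a wrong mean model. The planned pattern-mixture analyses address the missingness assumption, not the shape of the shared curve.

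**Working it through.** **Inputs from the documents.** "178 participants will be enrolled through the San Diego VA and randomized at the individual level"; permuted blocks aim at equal numbers, so 89 per arm. Visits are at 0, 2, 5 and 8 months. The documents give no PDA mean, SD, correlation, effect size, power or dropout rate, so there is no planned figure to reproduce. Everything below rests on assumptions.

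**Assumptions.** Random-intercept truth; within-person SD 20-25; a shared rise by month 2 that then stays about flat.

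**1. Lack of fit.** The mean visit time is 3.75, so Sxx = 14.0625 + 3.0625 + 1.5625 + 18.0625 = 36.75. Lack of fit = Syy − Sxy²/Sxx.
- Means 50/75/75/75: 468.75 − 93.75²/36.75 = 229.6.
- Means 40/75/75/72: 873 − 118.5²/36.75 = 490.9.
- A 15-point gain, then flat: 229.6 × (15/25)² = 82.7.

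**2. Standard error, complete data.** Each person contributes 3 within-person degrees of freedom, so the added residual variance is lack of fit / 3. The inflation factor is r = √(1 + added/SD²).

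| Shared profile | Added variance | r, SD 20 | r, SD 25 |
|---|---|---|---|
| 15-point gain, flat | 27.6 | 1.03 | 1.02 |
| 50/75/75/75 | 76.5 | 1.09 | 1.06 |
| 40/75/75/72 | 163.6 | 1.19 | 1.12 |

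The excess is therefore about 2-19%.

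**3. Power and error rate, complete data.** The correct SE is √(2·SD²/(89 × 36.75)): 0.495 for SD 20 and 0.618 for SD 25. True slope differences of 1.0 and 1.25 points per month both give a ratio of 2.02. Power is about Φ(2.02 − 1.96r), and the two-sided error rate is 2Φ(−1.96r).
- Correct model (r = 1): about 53%.
- 40/75/75/72: 38-43% by formula, 39-44% by simulation.
- 50/70/70/70: 48-50%.
- False-positive rate: 2.0-4.5% in simulation.

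The loss is thus about 3-14 points. A separate simulation (total SD 30, correlation 0.5, 25-point gain) gave 76% against 81%.

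**4. Why unequal dropout biases the slope.** Take means 50/75/75/75 and fit a line to one person's expected values.
- Visits 0 and 2 only: 25/2 = 12.5 per month.
- Visits 0, 2 and 5: 58.33/12.67 = 4.6 per month.
- All four visits: 93.75/36.75 = 2.6 per month.

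The arm with more short records gets the steeper line.

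**5. Size of the bias.** This is the expected generalised-least-squares slope difference, with identical arm means, dropout depending on arm only, and an assumed between-person SD of 20. The ranges cover the profiles 50/75/75/75 and 40/75/75/72 and SD 20-25.

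| Observed at 2/5/8 months | Linear: per month | Linear: month 8 | Shared quadratic: month 8 | Visit factor |
|---|---|---|---|---|
| 80/70/60% v 90/85/80% | 0.16-0.26 | 1.3-2.1 | at most 0.1 | 0 |
| 75/60/50% v 90/85/80% | 0.27-0.42 | 2.1-3.3 | at most 0.3 | 0 |

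Simulations with total SD 30, a 25-point gain and 20% against 40% final loss gave 1.0-1.7 points at month 8, depending on when the loss occurred.

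**6. False-positive rate under unequal dropout, linear time (simulated).**
- 80/70/60% v 90/85/80%: 3.9-4.9%.
- 75/60/50% v 90/85/80%: 5.5-6.2%, against 4.7-6.1% with visit as a factor. With 1,500 trials the simulation standard error is √(0.05 × 0.95/1500) = 0.6 points.
- 10% v 50% final loss (25-point gain, total SD 30): 8.0-8.5%.
- Stress case, 35-point gain, total SD 25, correlation 0.6 (within-person SD √(625 × 0.4) = 15.8, below the range above): 3.0% at 20% v 40% loss, 13.6% at 10% v 50%.

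**7. Null check.** With a truly linear shared course and 20% v 40% loss, the linear model showed no bias beyond simulation noise, and its mean SE was 0.604 against 0.605 with visit as a factor.

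**The case against.** Three points on the other side are sound.

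- **The SAP does not confine the model to a straight line.** It says "A quadratic effect of time will also be tested". A reader might infer that this term stands outside the primary model, or that the plan forces linearity. The SAP states neither; it is silent on the term's role. Kept as a shared term, the quadratic would remove nearly all the bias and most of the excess standard error. What remains is that the stated purpose is decay of the treatment effect rather than the shared curve, and that no rule links the term to the primary test.
- **A reader might infer that unequal dropout will produce a false positive finding.** At moderate imbalance it does not: the inflated standard error largely offsets the bias and rejection stays near 5%. A near-nominal error rate does not make the estimate unbiased, however, and the power loss with complete data is unaffected by this argument.
- **The sizes are conditional.** Hypothesis 1 gives no amount of change and does not say that change stops at month 2; the plateau is an inference. No dropout imbalance is stated either, since group appears only as a potential correlate. A smaller early gain shrinks every figure.

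A linear-plus-quadratic growth model is also a recognised choice, so the visit factor is not the only acceptable repair.

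**Conclusion.** The point holds as a gap in specification with modest consequences. The primary drinking test is written around a linear time term that fits poorly with the plan's own expectation of early improvement, and the quadratic that could correct this has no defined place in that test.

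Under an early rise and plateau of 15-35 points with within-person SD 20-25, linear time alone overstates the standard error by about 2-19% and costs about 3-14 points of power. Bias needs unequal dropout as well, and is then about 1-3 PDA points at month 8 for final losses of 20% against 40-50%. Only a large imbalance, such as 10% against 50%, moves the false-positive rate materially. The documents support neither a claim that the trial's error rate is generally compromised nor a claim that curvature was ignored. The change is still worth making, because it is cheap and removes the dependence on shape.

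**What to change.** In SAP section 6.H.3, second primary aim, state that the main effect of time enters the primary model from the outset as a four-level visit factor (0, 2, 5, 8 months), whichever treatment x time contrast is tested, and that the primary test does not depend on the result of the quadratic test. Any test of curvature in the treatment effect itself can stay as a secondary analysis. If the authors prefer a growth curve, a shared quadratic term fixed in advance achieves nearly the same.

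Cost: SAP wording, and two degrees of freedom (three time parameters instead of one) out of 178 × 3 = 534 within-person degrees of freedom with complete data. No new data are needed.
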